7.2.3. Suspected unexpected serious adverse reactions (SUSARs)

Not applicable

7.3. Annual safety report

Not applicable

7.4. Follow-up of adverse events

All AEs will be followed until they have abated, or until a stable situation has been reached. Depending on the event, follow up may require additional tests or medical procedures as indicated, and/or referral to the general physician or a medical specialist. SAEs need to be reported till the end of study within the Netherlands, as defined in the protocol.

7.5. [Data Safety Monitoring Board (DSMB) / Safety Committee]

Not applicable, this pilot study of 100 patients is expected to close within two years. When a larger trial follows this pilot, data safety monitoring will be necessary.

Due to recent literature, it is expected that prehabilitation in all patients undergoing major surgery should be standard care. The initiation of preoperative training in patients does not involve the nature of the disease and it is not expected to harm patients. On the contrary, subjects will enlarge their fitness and increase their capabilities to contact the hospital with the Luscii app.

In the annual progress report inclusion and complications of the operations will be reported to the METc UMCG.

Version number: 4 26 of 41

8. STATISTICAL ANALYSIS

8.1. Primary study parameter(s)

Comparison of patient characteristics between improved and non-improved patients, in relation to VO2 at VAT, will be done using a multivariable analysis. Data will be presented as mean and standard deviation or as median and interquartile range, as appropriate.

Categorical data will be summarized by frequency and percentage within each cohort. The comparison of improved and non-improved patients will be done with an multivariable regression analysis.

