UAVG Dutch Act on Implementation of the General Data Protection Regulation;

in Dutch: Uitvoeringswet AVG

VAT Ventilatory Anaerobic Threshold

WMO Medical Research Involving Human Subjects Act; in Dutch: Wet Medisch-

wetenschappelijk Onderzoek met Mensen

SUMMARY

Rationale: An aneurysm of the abdominal aorta (AAA) is a potentially life-threatening condition. Growth control and preventive surgery are important. It is proven safe to train patients with an AAA aiming to enhance aerobic fitness and improve surgical outcomes. Hypothesis: Training of patients awaiting their surgery for an AAA improves preoperative aerobic fitness. However, not all patients will improve their aerobic fitness following these training sessions.

Objective: The main objective is to separate patients who benefit from training from patients who do not benefit from training in terms of the change in CoF. The secondary objective is to study if training leads to change of aerobic fitness (CoF) in AAA patients after supervised training with a patient-specific training program. Feasibility of the study will be evaluated as well.

Study design: This is a single-arm intervention study. Patients, elected for AAA surgery, are invited to participate in this study. After inclusion, patients' socio-economic and personal characteristics are collected in a questionnaire, as well as their comorbidities (frailty-score, daily activities, ASA-score, dietary habits). All included patients will train at home under the responsibility of the principal investigator and the remote supervision of a specialist in sports medicine and a physical therapist, using home monitoring by means of the Luscii app. **Study population:** Patients with an indication for elective AAA surgery (endovascular and open surgery). Excluded are patients with AAA and an urgent (within less than 3 weeks) repair of the aneurysm and ruptured or symptomatic patients. Patients with genetic connective tissue disorders (e.g., Marfan) and patients unable to train will be excluded as well

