Several trials have established exercise training to be safe in people with AAA and training does not seem to influence aneurysm growth (8-11). Professional supervision (e.g., physical therapy and in-hospital aerobic exercise training) is expensive. Home-based monitoring of exercising patients with AAA is less expensive, and device handling by patients has been positively evaluated before (12).

This study is designed to investigate whether patients with AAA can improve their preoperative aerobic fitness during 3- to 9-week (6 weeks on average) training program. It is primarily designed to evaluate which patients benefit most from this program, based on three outcome measures: initial fitness (CPET), BMI and age. Home training will be performed with home-monitoring and weekly support by a physical therapist.

A successful six-week training program is a true investment, and some patients will not be able to benefit from it. At this point we are unable to select patients who will benefit most. Improvement of aerobic fitness probably depends on a combination of patient specific factors, e.g., age and sex, comorbidity, aerobic fitness at the start of the training, dietary habits, comorbidity, SES, frailty index, ASA-score, physical strength, and the available social support. Training specific factors play a role as well, such as the number of prescribed training sessions, intensity, and the duration. This study is designed to select patients who will benefit most from training, based upon their initial fitness, their BMI and their age. Patients with an AAA and an indication for operative repair were often male smokers, with high blood pressure, and lipid profiles (1). Depending on their diligence, recruitment rate, adherence, completion, drop-out, and attrition rate, will be important. These rates will be evaluated in relation to SES and other characteristics. During training, patients will be supported with dietary substitutes, in order to maintain an anabolic condition (13). Due to the training at home, the Luscii app (CE-certificate 0476) enables patients to ask questions and this might stimulate them to start training, under the suggestion to be observed by the call center.

OBJECTIVES

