Primary Objective: To compare patient characteristics between patients with clear improvement (more than 1.5 ml/kg/min improvement in the VO2 at VAT) after a three-to-nine-week training program, with patient characteristics of those who do not improve after training We aim to identify three factors that predict responsiveness to improve preoperative aerobic fitness following the training program.

Secondary objective: To evaluate the preliminary effectiveness of an, on average, six-week home-monitored training program, in patients with AAA scheduled for elective AAA-repair to improve the preoperative VO2 at the ventilatory anaerobic threshold (VAT).

Other Secondary Objective(s):

Other secondary aims are to evaluate the feasibility of this three-to-nine-week homemonitored training program. A fall-out of some patients is expected because physical exercise requires perseverance and endeavor. This feasibility is evaluated with:

- recruitment rate (how many patients will consent to participate in relation to the patients refusing participation).
- adherence rate (how many patients will endure participation in relation to the patients who give up participation, a.k.a. dropout rate) (Appendix 1).
- completion rate (how many patients will complete participation in relation to the number of patients ending participation).
- drop-out rate (how many patients will drop out of participation in relation to the number of patients completing participation).
- Attrition rate (how many patients will ask if a transfer to another treatment facility is possible, a.k.a. churn rate).

Additionally, the individual (preliminary) effect of prehabilitation on other CPET variables will be evaluated, such as VO₂ at peak exercise (VO_{2peak}) and the oxygen uptake efficiency slope, individual response profiles on the progression in aerobic fitness, improvement of the steep ramp test throughout the program. (Appendix 2).

The postoperative course in patients after AAA repair will be described as well, by collecting data on the surgical intervention and postoperative outcomes (e.g., hospital length of stay (HLOS), number of complications, mortality rate, readmission rate).

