2.4. Sample size calculation

A multivariable regression analysis will be performed to identify important risk factors, such as a low fitness at the beginning of the training, a low or high BMI ($20 \ge BMI \ge 31$), and a low or high age ($50y \ge age \ge 90y$)(18). With the rule of thumb requiring 10 subjects per variable, and a chance of improvement of 50% (3 variables (fitness t= 0, BMI, and age) x 10 subjects x 0,5= 60); 60 patients will be required to include. Inclusion of one hundred patients will be necessary to perform a multivariable regression analysis with three variables, assuming an exclusion rate of 20%, and a drop-out rate of 20%. Three small sample, randomized controlled trials showed higher VO2 at VAT after 3, 6, or

9 weeks of training in gastroenterological cancer patients, patients with AAA, and rectal cancer patients, respectively: of 10,1%; 18%; or 29% (Table 1)(11, 19, 20).

Version number: 4

Study	Inclusion	n	Wks	% Impro-	VO2	SD	95%CI	VO2	SD	95%CI	ΔVO2
				vement	t=0			t=1			
Berkel(19)	GE-patients	28	3	10,1	9,6	1,2	9,1 - 10,1	10,5	1,36	10 - 11,1	0,9
Barakat(11)	AAA patients	20	6	18	12,2		10,5 - 14,9	14,4		12,3 - 15,4	2,2
Loughney(20)	Rectal CA	17	9	29	11,6	3,4	9,9 - 13,3	15	4,2	12,7 - 17,3	3,4
	total	65			•						

Table 1. Three randomized controlled trials evaluating fitness after training. Wks= weeks, SD= standard deviation, GE= gastroenterological, AAA= abdominal aorta aneurysm, and CA= cancer.

These patients reached an improvement ranging from 0.9 ml/kg/min up to 3.4 ml/kg/min (assumed mean 1.5 ml/kg/min). When subdividing the group of patients into a group with increased fitness (> 1.5 ml/kg/min) and a group without increased fitness (≤ 1.5 ml/kg/min), a dichotomous outcome is reached.

The multivariable analysis will be performed with other patient specific characteristics, as well, such as comorbidities. Modifiable factors will be analyzed as well, such as dietary habits, social economic status, frailty score, and other information collected in the questionnaires.

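### The stated aim of separating and selecting responders goes further than the comparison of characteristics planned in section 8.1, and the two should be aligned

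*Protocol*

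**What the plan says.** The protocol describes its main aim in two ways.

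**As separation, selection or prediction.**
- Summary, Objective: "The main objective is to separate patients who benefit from training from patients who do not benefit from training".
- Introduction and rationale: "This study is designed to select patients who will benefit most from training, based upon their initial fitness, their BMI and their age".
- Objectives, second sentence of the primary objective: "We aim to identify three factors that predict responsiveness to improve preoperative aerobic fitness following the training program".
- Section 3.1 adds that future surgical strategies need patients who can improve to be identified beforehand by questionnaire.

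**As a comparison of groups.**
- Objectives, first sentence: "To compare patient characteristics between patients with clear improvement (more than 1.5 ml/kg/min improvement in the VO2 at VAT"), set against the characteristics of those who do not improve.
- The main endpoint in the Summary and the text of section 6.2 are also comparisons of improved with non-improved patients.

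Section 8.1 follows the second description: descriptive summaries, then "The comparison of improved and non-improved patients will be done with an multivariable regression analysis". Section 2.4 splits the change in VO2 at VAT at 1.5 ml/kg/min, so that "a dichotomous outcome is reached", and sizes the study for three variables. It then says that comorbidities will enter the multivariable analysis too, and that diet, socio-economic status, frailty and other questionnaire items will be analysed as well.

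**The concern.** Whether a factor differs between improvers and non-improvers is one question. Whether the factors can tell beforehand who will improve is another. The first is answered by a coefficient and its p-value, the second by a measure of discrimination and by agreement between predicted and observed chances. Followed as written, 8.1 yields only the first.

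A second difficulty comes from the sample size. A model judged in the patients used to fit it looks better than it will in others, and with 30 improvers and 30 non-improvers the gap is not negligible.

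At stake is the main conclusion. A significant odds ratio could be reported as evidence that patients can be selected for prehabilitation when the factors separate them only weakly.

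**Working it through.** **Inputs from section 2.4.** Three variables (initial fitness, BMI, age); "With the rule of thumb requiring 10 subjects per variable, and a chance of improvement of 50"%; "60 patients will be required to include". The threshold of 0.05 is given in section 8.2.

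**The plan's own figures.** 3 × 10 / 0.5 = 60, which matches. (The operation as printed, 3 × 10 × 0.5, gives 15; the result is right only as a division.) Adding the 20% exclusion and 20% drop-out gives 60 / (1 − 0.40) = 100, which also matches. The analysis set is therefore 60 patients, with 60 × 0.5 = 30 improvers.

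**Association against separation (assumed effect).** Take one factor with an odds ratio of 2.0 per SD; ln 2.0 = 0.693.
- Approximate power, two-sided 0.05: Φ(0.693 × √(60 × 0.25) − 1.96) = Φ(2.68 − 1.96) = Φ(0.72) ≈ 0.77. This ignores the other two variables. Simulating the three-variable model, with the other two as noise, gives 68%.
- c-statistic of that factor: Φ(0.693 / √2) = Φ(0.49) ≈ 0.69; by simulation 0.68.
- Splitting patients at the median of that factor: P(improve | upper half) = ∫ 2φ(x) · expit(0.693x) dx over x > 0 = 0.63, against 0.37 in the lower half.
- The fitted three-variable model shows c of 0.71 in its own data and 0.65 in new patients, with a calibration slope of about 0.66.

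Such a factor would be significant in roughly seven trials out of ten while separating patients only moderately.

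**Optimism over a range of assumed truths.** Logistic regression, n = 60, 50% improving, three independent normal predictors all carrying signal (none in the first row), 800 runs per row, tested in 4,000 new patients. The excess is computed before rounding.

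| True c | Apparent c | c in new patients | Excess | Median calibration slope |
|---|---|---|---|---|
| 0.50 | 0.621 | 0.500 | 0.121 | 0.00 |
| 0.65 | 0.684 | 0.617 | 0.067 | 0.57 |
| 0.70 | 0.726 | 0.673 | 0.052 | 0.72 |
| 0.75 | 0.769 | 0.732 | 0.036 | 0.77 |
| 0.80 | 0.817 | 0.778 | 0.038 | 0.78 |

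Each row uses one set of 4,000 new patients. The standard error of c in such a set is about 0.063 × √(30/2000) = 0.008, so differences of 0.01 between rows mean nothing.

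**If further variables enter, as section 2.4 allows.** Same setting, with the added predictors as noise:
- Six predictors: excess 0.08 to 0.14 for true c of 0.80 to 0.65, and 0.17 with no signal.
- Ten predictors: excess 0.13 to 0.19, and 0.23 with no signal; slopes 0.43 to 0.21.

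**Precision of c with 30 against 30 (Hanley–McNeil).** At A = 0.70, A/(2 − A) = 0.538 and 2A²/(1 + A) = 0.576. The variance is [0.21 + 29 × (0.538 − 0.49) + 29 × (0.576 − 0.49)] / 900 ≈ 0.0046, so SE ≈ 0.068 and the 95% CI is 0.57 to 0.83. At A = 0.75 it is 0.63 to 0.87.

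**The case against.** The best defence is that 8.1 does match a stated primary objective. The first sentence under Objectives, the main endpoint in the Summary and section 6.2 all describe a comparison, and identifying predictive factors by multivariable regression is common practice. This stands in part. A reader might infer that the primary analysis misses the primary objective altogether; the documents do not support that. The mismatch is with the Summary's objective, the Introduction and the second sentence under Objectives.

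It can also be said that c-statistics, bootstrap settings and shrinkage belong in a statistical analysis plan, which is not at hand, and that a regression on a binary outcome yields predicted probabilities anyway. This stands too: the absence of those mechanics is not in itself a fault, and nothing in 8.1 prevents them. What remains is that the protocol announces selection as its purpose and fixes a primary analysis that does not call for any measure of it.

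Finally, the study calls itself a pilot (sections 6.3 and 7.5) and proposes no cut-off, risk score or transfer of coefficients to new patients. A reader might infer that an unvalidated selection rule is about to be put into use; the text does not say so. The pilot status argues for modest claims, which is a reason to bring the stated aim and the analysis into line.

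**Conclusion.** The point holds as a mismatch within the protocol: three statements aim at separating, selecting or predicting, while 8.1 and the remaining statements plan a comparison.

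The size of the optimism rests on assumed effects, because the documents give no odds ratio, c-statistic or R². With three informative, independent predictors and 60 patients it is modest: about 0.04 to 0.07 in c for true values of 0.65 to 0.80, with slopes of about 0.6 to 0.8. It is about 0.12 when there is no signal, which is where a mistaken claim that patients can be selected does most harm. It would be tempting to call the planned model grossly over-fitted, but the three-variable figures do not show that. The larger excess appears only if the open list in section 2.4 enters the same model. The change is advisable and does not affect the conduct of the study.

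**What to change.** In section 8.1:
- Name one logistic model of improvement on the three prespecified factors (initial fitness, BMI, age) as the primary analysis.
- Report its c-statistic with a 95% CI and its calibration slope, both corrected for optimism by bootstrap. The technical settings can go in the analysis plan.
- Label models with comorbidities, diet, socio-economic status, frailty and other items exploratory.
- Limit any claim about selecting patients to what the corrected performance supports.

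If the team prefers to keep 8.1 as it is, the alternative is to reword the Summary's objective and the Introduction, and for consistency the predictive sentence under Objectives, as exploratory association.

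Two additions are not advised. A success rule that the lower confidence limit of c must exceed 0.5 only tests against no discrimination again. In 250 simulated trials with the single-factor effect above, it was met in 58%, against 65% in which the factor was significant. Compulsory shrinkage by the bootstrap slope would be unstable at this size, since that slope ran from 0.41 to 0.87 (5th to 95th percentile) in the same simulations.

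The cost is one paragraph in 8.1 and a few hours of analysis, with no extra patients, visits or data. The downside is that the reported performance will look less favourable and less certain.

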8.2. Secondary study parameter(s)

To measure if patients with an indication for AAA-repair can improve their VO2 at VAT. The second measurement will be performed after a three to nine week training program, using the advice of a specialist in sports medicine, consults of a physical therapist and eHealth monitoring. To evaluate the effectiveness of the, on average, six-week home-monitored prehabilitation program, the difference in the VO2 at the ventilatory anaerobic threshold before the start of the training and after an average six weeks of prehabilitation will be analyzed using a paired samples t-test or Wilcoxon signed rank test, as appropriate. A repeated measurements analysis (mixed models in SPSS) will be performed to assess changes over time in continuous variables. P values <0.05 will be considered statistically significant. Modifiable factors will be analyzed as well, such as dietary habits, social economic status, frailty score, and other information collected in the questionnaires.

To evaluate the feasibility of the average six-week home-monitored prehabilitation program, adherence or compliance, adverse events, motivation, and patient appreciation will be described by use of descriptive statistics. Descriptive statistics will be used to present data on perioperative variables and postoperative progress.

8.3. Other study parameters

Not applicable.

8.4. Interim analysis (if applicable)

Not applicable

Version number: 4 27 of 41

9. ETHICAL CONSIDERATIONS

9.1. Regulation statement

We will perform all study procedures according to the Declaration of Helsinki, the Medical Research Involving Human Subjects Act (in Dutch: Wet Medisch-wetenschappelijk Onderzoek met Mensen [WMO]) and the Dutch Personal Data Protection Act.

9.2. Recruitment and consent

At the indication for AAA repair, patients will be informed by the treating vascular surgeon. Patients will receive an information document from their treating physician. Eligible subjects receive an appointment with the (co)investigator within one week. When they agree during an appointment with the (co)investigator, patients need to sign a declaration of informed consent. Eligible patients will be given a minimum of 24 hours, and a maximum of 2 weeks, to determine participation. When informed consent is signed, all subjects will complete the questionnaire and will perform a CPET. Bases upon the result of these tests the cardiac evaluation is made, if necessary complemented by other diagnostics. After training and during their surgery, patients will be followed until 30 days hereafter (Figure 1).

9.3. Objection by minors or incapacitated subjects (if applicable)

Not applicable

9.4. Benefits and risks assessment, group relatedness

Not applicable

9.5. Compensation for injury

For all research sites liability insurances are provided for the principal investigator has a liability insurance which is in accordance with article 7 of the WMO. The sponsor has an insurance which is in accordance with the legal requirements in the Netherlands (Article 7 WMO). These insurances provide coverage for damage to research subjects through injury or death caused by the study. The insurances apply to the damage that becomes apparent during the study or within 4 years after the end of the study.

9.6. Incentives (if applicable)

Not applicable

Version number: 4 28 of 41

10. ADMINISTRATIVE ASPECTS, MONITORING AND PUBLICATION

10.1. Handling and storage of data and documents

Patient data will be handled in correspondence with the EU General Data Protection Regulation and the Dutch Act on Implementation of the General Data Protection Regulation. Data will be stored analogue in pseudonymised case report forms (CRF). Pseudonymisation will be performed using a code, and besides name, date of birth and sex, we will not register personal details in the decoding list. The code will be formed by a number appointed to the site of inclusion, the year and month, and the chronologic order of patients included in the center of inclusion. The key document to the codes will be kept on a secured server at each location under the responsibility of the local investigator. Data is stored for 15 years.

10.2. Monitoring and Quality Assurance

The CE certificate of the Luscii app describes the following about data management: "Clinical engine software for remote patient monitoring", data will be stored in the cloud maintained according to ISO standards in AWS data centers in Frankfurt (Germany); mentioned at the Luscii website. These data are supervised by a medical officer, aka the designated Data Controller. Data will be stored according to the rules of the new privacy legacy and guaranteeing the GDPR (General Data Protection Regulation).

